#### **6.2.1 Expedited Reporting**

Expedited reporting will be conducted in accordance with FHCRC/Cancer Consortium IRB policies, applicable FDA regulations.

### **6.3 Overdose and Reporting Requirements**

For purposes of this study, an overdose of pembrolizumab will be defined as any dose of 1,000 mg or greater ( $\geq 5$  times the indicated dose). No specific information is available on the treatment of overdose of pembrolizumab. In the event of overdose, the participant should be observed closely for signs of toxicity. Appropriate supportive treatment should be provided if clinically indicated.

If an adverse event(s) is associated with (“results from”) the overdose of a Merck product, the adverse event(s) is reported as a serious adverse event, even if no other seriousness criteria are met.

If a dose of Merck’s product meeting the protocol definition of overdose is taken without any associated clinical symptoms or abnormal laboratory results, the overdose is reported as a non-serious Event of Clinical Interest (ECI), using the terminology “accidental or intentional overdose without adverse effect.”

All reports of overdose with and without an adverse event must be reported within 24 hours to the Sponsor and within 2 working days hours to Merck Global Safety. (Attn: Worldwide Product Safety; [contact])

#### **6.3.1 Reporting of Pregnancy and Lactation to the Sponsor and to Merck**

Although pregnancy and infant exposure during breast feeding are not considered adverse events, it is the responsibility of investigators or their designees to report any pregnancy or lactation in a participant (spontaneously reported to them) that occurs during the study.

Pregnancies and infant exposures during breastfeeding that occur after the consent form is signed but before treatment allocation/randomization must be reported by the investigator if they cause the participant to be excluded from the trial, or are the result of a protocol-specified intervention, including but not limited to washout or discontinuation of usual therapy, diet, placebo treatment or a procedure.

Pregnancies and infant exposures during breastfeeding that occur from the time of treatment allocation/randomization through 120 days following cessation of Sponsor's product, or 30 days following cessation of treatment if the participant initiates new anticancer therapy, whichever is earlier, must be reported by the investigator. All reported pregnancies must be followed to the completion/termination of the pregnancy. Pregnancy outcomes of spontaneous abortion, missed abortion, benign hydatidiform mole, blighted ovum, fetal death, intrauterine death, miscarriage and stillbirth must be reported as serious events (Important Medical Events). If the pregnancy continues to term, the outcome (health of infant) must also be reported.

Such events must be reported within 24 hours to the Sponsor and within 2 working days to Merck Global Safety. (Attn: Worldwide Product Safety; [contact])

### **6.3.1.1 Events of Clinical Interest**

Selected non-serious and serious adverse events are also known as Events of Clinical Interest (ECI) and must be reported within 2 working days to Merck Global Safety. (Attn: Worldwide Product Safety; [contact]).

For the time period beginning when the consent form is signed until treatment allocation/randomization, any ECI, or follow up to an ECI, that occurs to any participant must be reported within 2 working days to Merck Global Safety if it causes the participant to be excluded from the trial, or is the result of a protocol-specified intervention, including but not limited to washout or discontinuation of usual therapy, diet, placebo treatment or a procedure.

For the time period beginning at treatment allocation/randomization through 90 days following cessation of treatment, or 30 days following cessation of treatment if the participant initiates new anticancer therapy, whichever is earlier, any ECI, or follow up to an ECI, whether or not related to Merck product, must be reported within 2 working days to Merck Global Safety.

Events of clinical interest for this trial include:

1. an overdose of Merck product, as defined in Section 6.3- Definition of an Overdose for This Protocol and Reporting of Overdose to the Sponsor, that is not associated with clinical symptoms or abnormal laboratory results.

2. an elevated AST or ALT lab value that is greater than or equal to 3X the upper limit of normal and an elevated total bilirubin lab value that is greater than or equal to 2X the upper limit of normal and, at the same time, an alkaline phosphatase lab value that is less than 2X the upper limit of normal, as determined by way of protocol-specified laboratory testing or unscheduled laboratory testing.\*

**\*Note:** These criteria are based upon available regulatory guidance documents. The purpose of the criteria is to specify a threshold of abnormal hepatic tests that may require an additional evaluation for an underlying etiology.

#### **6.3.1.1.1 Evaluating Adverse Events**

Table 7 Evaluating Adverse Events

An investigator who is a qualified physician, will evaluate all adverse events as to:

V4.0 CTCAE Grading	Grade 1	Mild; asymptomatic or mild symptoms; clinical or diagnostic observations only; intervention not indicated.
	Grade 2	Moderate; minimal, local or noninvasive intervention indicated; limiting age-appropriate instrumental ADL.
	Grade 3	Severe or medically significant but not immediately life-threatening; hospitalization or prolongation of hospitalization indicated; disabling; limiting self-care ADL.
	Grade 4	Life threatening consequences; urgent intervention indicated.
	Grade 5	Death related to AE
Seriousness	A serious adverse event is any adverse event occurring at any dose or during any use of Merck product that:	
	† Results in death; or	
	† Is life threatening; or places the participant, in the view of the investigator, at immediate risk of death from the event as it occurred (Note: This does not include an adverse event that, had it occurred in a more severe form, might have caused death.); or	
	† Results in a persistent or significant disability/incapacity (substantial disruption of one's ability to conduct normal life functions); or	
	† Results in or prolongs an existing inpatient hospitalization (hospitalization is defined as an inpatient admission, regardless of length of stay, even if the hospitalization is a precautionary measure for continued observation. (Note: Hospitalization for an elective procedure to treat a pre-existing condition that has not worsened is not a serious adverse event. A pre-existing condition is a clinical condition that is diagnosed prior to the use of a Merck product and is documented in the patient's medical history.); or	
	† Is a congenital anomaly/birth defect (in offspring of participant taking the product regardless of time to diagnosis); or	
	Is a new cancer (that is not a condition of the study) (although not serious per ICH definition, is reportable to the Sponsor within 24 hours and to Merck within 2 working days to meet certain local requirements); or	
	Is an overdose (whether accidental or intentional). Any adverse event associated with an overdose is considered a serious adverse event for collection purposes. An overdose that is not associated with an adverse event is considered a non-serious event of clinical interest and must be reported within 24 hours to the Sponsor and to Merck within 2 working days..	

	Other important medical events that may not result in death, not be life threatening, or not require hospitalization may be considered a serious adverse event when, based upon appropriate medical judgment, the event may jeopardize the participant and may require medical or surgical intervention to prevent one of the outcomes listed previously (designated above by a †).						
Duration	Record the start and stop dates of the adverse event. If less than 1 day, indicate the appropriate length of time and units						
Action taken	Did the adverse event cause Merck product to be discontinued?						
Relationship to Merck Product	
Did Merck product cause the adverse event? The determination of the likelihood that Merck product caused the adverse event will be provided by an investigator who is a qualified physician. The investigator's signed/dated initials on the source document or worksheet that supports the causality noted on the AE form, ensures that a medically qualified assessment of causality was done. This initialed document must be retained for the required regulatory time frame. The criteria below are intended as reference guidelines to assist the investigator in assessing the likelihood of a relationship between the test drug and the adverse event based upon the available information.
 
The following components are to be used to assess the relationship between Merck product and the AE; the greater the correlation with the components and their respective elements (in number and/or intensity), the more likely Merck product caused the adverse event (AE):
 
 
 Exposure	Is there evidence that the participant was actually exposed to Merck product such as: reliable history, acceptable compliance assessment (pill count, diary, etc.), expected pharmacologic effect, or measurement of drug/metabolite in bodily specimen?	
 
 Time Course	Did the AE follow in a reasonable temporal sequence from administration of Merck product? Is the time of onset of the AE compatible with a drug-induced effect (applies to trials with investigational medicinal product)?	
 
 Likely Cause	Is the AE not reasonably explained by another etiology such as underlying disease, other drug(s)/vaccine(s), or other host or environmental factors	
 
	Exposure	Is there evidence that the participant was actually exposed to Merck product such as: reliable history, acceptable compliance assessment (pill count, diary, etc.), expected pharmacologic effect, or measurement of drug/metabolite in bodily specimen?	Time Course	Did the AE follow in a reasonable temporal sequence from administration of Merck product? Is the time of onset of the AE compatible with a drug-induced effect (applies to trials with investigational medicinal product)?	Likely Cause	Is the AE not reasonably explained by another etiology such as underlying disease, other drug(s)/vaccine(s), or other host or environmental factors
Exposure	Is there evidence that the participant was actually exposed to Merck product such as: reliable history, acceptable compliance assessment (pill count, diary, etc.), expected pharmacologic effect, or measurement of drug/metabolite in bodily specimen?						
Time Course	Did the AE follow in a reasonable temporal sequence from administration of Merck product? Is the time of onset of the AE compatible with a drug-induced effect (applies to trials with investigational medicinal product)?						
Likely Cause	Is the AE not reasonably explained by another etiology such as underlying disease, other drug(s)/vaccine(s), or other host or environmental factors						

Relationship to Merck Product (continued)	The following components are to be used to assess the relationship between the test drug and the AE: (continued)	
	Dechallenge	
Was Merck product discontinued or dose/exposure/frequency reduced?
 
If yes, did the AE resolve or improve?
 
If yes, this is a positive dechallenge. If no, this is a negative dechallenge.
 
(Note: This criterion is not applicable if: (1) the AE resulted in death or permanent disability; (2) the AE resolved/improved despite continuation of the Sponsor's product; or (3) the trial is a single-dose drug trial); or (4) Sponsor's product(s) is/are only used one time.)

	Rechallenge	
Was the participant re-exposed to Merck product in this study?
 
If yes, did the AE recur or worsen?
 
If yes, this is a positive rechallenge. If no, this is a negative rechallenge.
 
(Note: This criterion is not applicable if: (1) the initial AE resulted in death or permanent disability, or (2) the trial is a single-dose drug trial); or (3) Sponsor's product(s) is/are used only one time).
 
NOTE: IF A RECHALLENGE IS PLANNED FOR AN ADVERSE EVENT WHICH WAS SERIOUS AND WHICH MAY HAVE BEEN CAUSED BY MERCK PRODUCT, OR IF REEXPOSURE TO MERCK PRODUCT POSES ADDITIONAL POTENTIAL SIGNIFICANT RISK TO THE PARTICIPANT, THEN THE RECHALLENGE MUST BE APPROVED IN ADVANCE BY THE SPONSOR AS PER DOSE MODIFICATION GUIDELINES IN THE PROTOCOL.

	Consistency with Trial Treatment Profile	Is the clinical/pathological presentation of the AE consistent with previous knowledge regarding Merck product or drug class pharmacology or toxicology?
The assessment of relationship will be reported on the case report forms /worksheets by an investigator who is a qualified physician according to his/her best clinical judgment, including consideration of the above elements.		
Record one of the following		Use the following scale of criteria as guidance (not all criteria must be present to be indicative of Merck product relationship).
Yes, there is a reasonable possibility of Merck product relationship.		There is evidence of exposure to Merck product. The temporal sequence of the AE onset relative to the administration of Merck product is reasonable. The AE is more likely explained by Merck product than by another cause.

No, there is not a reasonable possibility of Merck product relationship	Participant did not receive the Merck product OR temporal sequence of the AE onset relative to administration of Merck product is not reasonable OR the AE is more likely explained by another cause than the Merck product. (Also entered for a participant with overdose without an associated AE.)
--	---

### 6.3.2 Sponsor Responsibility for Reporting Adverse Events

A serious adverse event is any adverse event occurring at any dose or during any use of Merck's product that:

- Results in death;
- Is life threatening;
- Results in persistent or significant disability/incapacity;
- Results in or prolongs an existing inpatient hospitalization;
- Is a congenital anomaly/birth defect;
- Is another important medical event
- **Note:** In addition to the above criteria, adverse events meeting either of the below criteria, although not serious per ICH definition, are reportable to the Merck in the same timeframe as SAEs to meet certain local requirements. Therefore, these events are considered serious by Merck for collection purposes.
  - Is a new cancer (that is not a condition of the study);
  - Is associated with an overdose.

For the time period beginning when the consent form is signed until treatment allocation/randomization, any serious adverse event, or follow up to a serious adverse event, including death due to any cause that occurs to any participant must be reported within 24 hours to the Sponsor and within 2 working days to Merck Global Safety if it causes the participant to be excluded from the trial, or is the result of a protocol-specified intervention, including but not limited to washout or discontinuation of usual therapy, diet, placebo treatment or a procedure.

For the time period beginning at treatment allocation/randomization through 90 days following cessation of treatment, or 30 days following cessation of treatment if the participant initiates new anticancer therapy, whichever is earlier, any serious adverse event, or follow up to a serious adverse event, including death due to any cause whether or not related to the Merck product, must be reported within 24 hours to the Sponsor and within 2 working days to Merck Global Safety.

Additionally, any serious adverse event, considered by an investigator who is a qualified physician to be related to Merck product that is brought to the attention of the investigator at any time following consent through the end of the specified safety follow-up period specified in the paragraph above, or at any time outside of the time period specified in the previous paragraph also must be reported immediately to Merck Global Safety.

All participants with serious adverse events must be followed up for outcome.

**SAE reports and any other relevant safety information are to be forwarded to the Merck Global Safety [contact]**

A copy of all 15 Day Reports and Annual Progress Reports is submitted as required by FDA, European Union (EU), Pharmaceutical and Medical Devices agency (PMDA) or other local regulators. Investigators will cross reference this submission according to local regulations to the Merck Investigational Compound Number (IND, CSA, etc.) at the time of submission. Additionally, investigators will submit a copy of these reports to Merck & Co., Inc. (Attn: Worldwide Product Safety; [contact]) at the time of submission to FDA.

## **7.0 STATISTICAL ANALYSIS PLAN**

### **7.1 Statistical Analysis Plan**

#### **Part A:**

The primary objective of this study is to estimate the safety of 2 cycles of APVD. Historical data regarding the tolerability of 2 cycles of ABVD are limited. In a recent trial of AHD+ brentuximab vedotin, 4 of 26 (~15%) patients were reported to be unable to complete treatment [Connors et al. 2017]. We will be more conservatively scoring treatment delay due to toxicity rather than inability to complete the entire treatment course. Thus, we will deem this regimen safe if >85% of patients are able to complete 2 cycles of APVD without a dose delay of >3 weeks. This will be employed as a stopping rule and serve as the primary endpoint.

Operationally, the stopping rule will be activated if the lower limit of the 95% confidence interval of toxicity crosses 15%. Thus, the trial would stop if 4/10, 7/20, 8/25, or 9 of 30 had a dose delay of >3 weeks due to toxicity.

If the stopping rule is activated the trial will be paused and the data reviewed to determine if the results can be explained by the patient population (e.g., older, more comorbidities) or by the toxicity of the regimen. A report will be drafted for IRB review to either close the trial, modify and continue the trial, or continue the trial in an unmodified fashion. Since the study is not statistically powered for efficacy evaluation, the sample size justification is based on clinical evaluation on safety. If we use the stopping rule if 30% patients were unable to complete treatment, then the 95% confidence interval for the assumed toxicity rate with 30 patients are 17% to 48%, which excluded 15% assumed rate. With smaller sample size, the width of the 95% CI will be larger, e.g. 15% to 52% for 20 patients, 16% to 50% for 25 patients, etc. The larger sample size will also lead to stable point estimation, so it will increase the chance for a more accurate observation. We anticipate that 30 patients will be required to reasonably estimate the safety of this regimen as defined above. Furthermore, assume the incidence rate of toxicity is around 15%, with sample size N=30, we will have more than 85% chance of observing more than two patients not finishing the trial and 99% chance of observing at least one such patient (see table 1) Probability to observe at least 1 or 3 events having a dose delay due to toxicity, estimated for different incidence rates and sample size

Sample Size	Incidence rate of toxicity	PR (observe at least one events had a dose delay)	PR (observe at least three events had a dose delay)
30	0.1	96%	59%
30	0.15	99%	85%
25	0.1	93%	46%
25	0.15	98%	75%
20	0.1	88%	32%
20	0.15	96%	60%

In unpublished data, 28 patients have completed 2 cycles of APVD, and there were no delays in treatments of greater than 21 days in any of these patients. Therefore, even without information on the final 2 patients, it can be determined that the primary endpoint for part A of the study has been met.

**Part B:**

Based on the rationale outlined in the background section, we plan to enroll 20 additional patients in part B (for a total of 50 between part A and B). We will only accrue advanced stage patients (stage 3 or 4) for this portion of the study.

In part A, we have enrolled 29 patients, of whom 18 were stage 3 or 4. We expect the final patient in part A will be advanced stage, and therefore we expect to have 19 total advanced stage patients in Part A. When combined with expected accrual of 20 patients in Part B, we expect to have 39 total advanced stage patients that are evaluable for efficacy data.

Given our concerns with PET-based assessments, we will analyze the 39 advanced patients for efficacy by estimating 1-year EFS. An event will be defined as progression, biopsy proven recurrence, initiation of next line of chemotherapy, or death. The benchmark to deem this regimen as potentially efficacious will be 1-year EFS of 85% for this population (intermediate between the more commonly used ABVD and the more toxic but less commonly used brentuximab vedotin + AVD). Towards this end, we shall consider an observed 1-year EFS among the 39 patients of at least 0.85 (33 or more of 39) to be potentially efficacious and warrant further study of the current regimen (note that this will not necessarily imply a statistically significant improvement on this benchmark). The decision will also take into consideration secondary endpoints. The table below summarizes the probability of observing a 1-year EFS of at least 85% under a variety of assumed-true 1-year EFS values.

Assumed-true 1-year EFS	Probability of observed 1-year EFS of at least 85%
75%	0.11
80%	0.31
85%	0.63
90%	0.91

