### 3.4 Background

#### Efficacy and limitations of ABVD

ABVD (Doxorubicin, Bleomycin, Vinblastine, and Dacarbazine) is a component of a standard regimen in North America for treatment of classical Hodgkin's lymphoma (cHL) regardless of disease stage. It was originally developed in 1970, showed similar efficacy compared with MOPP regimen (Mechlorethamine, Vincristine, Procarbazine, and Prednisone) and more importantly had an improved tolerability and toxicity profile. In the advanced cHL setting, ABVD use offers up to 70% long term tumor control rate. However, up to 25% of patients do not respond completely to ABVD. Additionally, of the initial responders relapse occurs in a significant proportion of patients who then require salvage chemotherapy, high dose chemotherapy, autologous stem cell transplant, brentuximab-vedotin, nivolumab or pembrolizumab. Nevertheless, ABVD is still considered a standard frontline regimen for classical cHL despite the fact that up to one-third of patients will not be cured with this approach.

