#### Early activity of APVD

Accrual on this study began in February 2020, and as of May 21, 2021, 29 of the original 30 planned patients have been enrolled (unpublished data). We noted a CR rate of 65% on interim PET (slightly lower than previously presented in standard ABVD). 5 patients so far have had a positive PET at end of treatment, but only one patient so far has had evidence of progressive CHL. 80% (4/5) of patients with FDG uptake post treatment never progressed at 8, 9, 18, and 19 months. These patients were either followed with serial imaging with resolution or underwent a biopsy.

These findings raise concerns that traditional methods of PET response assessment may be prone to false positives in patients treated with checkpoint inhibitor combinations. For this reason, we will plan to treat an additional 20 advanced stage patients with this regimen in order to better assess the activity of this regimen using a 1-year EFS endpoint.

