#### **4.3.2 Prohibited Concomitant Medications**

The administration of concurrent medications intended to treat the primary cancer is not allowed during protocol therapy. This includes any chemotherapy, investigational agent, biologic agent or other anti-tumor agents. Radiation therapy is also prohibited.

Patients should be strongly discouraged from taking any "alternative" or "naturopathic" medications since these agents may interact with APVD.

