#### **6.1.1.4.3 Subsequent Anti-Cancer Therapy Status**

The investigator or qualified designee will review all new anti-neoplastic therapy initiated after the last dose of trial treatment.

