**Appendix 3: Response Criteria: “The Lugano Classification”**

Response and Site	PET-CT-Based Response	CT-Based Response
Complete	Complete metabolic response	Complete radiologic response (all of the following)
Lymph nodes and extralymphatic sites	Score 1, 2, or 3* with or without a residual mass on 5PS †  It is recognized that in Waldeyer's ring or extranodal sites with high physiologic uptake or with activation within spleen or marrow (eg, with chemotherapy or myeloid colony-stimulating factors), uptake may be greater than normal mediastinum and/or liver. In this circumstance, complete metabolic response may be inferred if uptake at sites of initial involvement is no greater than surrounding normal tissue even if the tissue has high physiologic uptake	Target nodes/nodal masses must regress to $\leq 1.5$ cm in LD $i$
Nonmeasured lesion	Not applicable	No extralymphatic sites of disease
Organ enlargement	Not applicable	Rgress to normal
New lesions	None	None
Bone marrow	No evidence of FDG-avid disease in marrow	Normal by morphology; if indeterminate, IHC negative
Partial	Partial metabolic response	Partial remission (all of the following)
Lymph nodes and extralymphatic sites	Score 4 or 5 † with reduced uptake compared with baseline and residual mass(es) of any size	$\geq 50\%$ decrease in SPD of up to 6 target measurable nodes and extranodal sites

Response and Site	PET-CT-Based Response	CT-Based Response
	At interim, these findings suggest responding disease	When a lesion is too small to measure on CT, assign 5 mm × 5 mm as the default value
	At end of treatment, these findings indicate residual disease	When no longer visible, 0 × 0 mm
		For a node > 5 mm × 5 mm, but smaller than normal, use actual measurement for calculation
Nonmeasured lesions	Not applicable	Absent/normal, regressed, but no increase
Organ enlargement	Not applicable	Spleen must have regressed by > 50% in length beyond normal
New lesions	None	None
Bone marrow	Residual uptake higher than uptake in normal marrow but reduced compared with baseline (diffuse uptake compatible with reactive changes from chemotherapy allowed). If there are persistent focal changes in the marrow in the context of a nodal response, consideration should be given to further evaluation with MRI or biopsy or an interval scan	Not applicable
No response or stable disease	No metabolic response	Stable disease

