Target nodes/nodal masses, extranodal lesions	Score 4 or 5 with no significant change in FDG uptake from baseline at interim or end of treatment	< 50% decrease from baseline in SPD of up to 6 dominant, measurable nodes and extranodal sites; no criteria for progressive disease are met

Response and Site	PET-CT-Based Response	CT-Based Response
Nonmeasured lesions	Not applicable	No increase consistent with progression
Organ enlargement	Not applicable	No increase consistent with progression
New lesions	None	None
Bone marrow	No change from baseline	Not applicable
Progressive disease	Progressive metabolic disease	Progressive disease requires at least 1 of the following
Individual target nodes/nodal masses	Score 4 or 5 with an increase in intensity of uptake from baseline and/or	PPD progression:  An individual node/lesion must be abnormal with: LDi > 1.5 cm and Increase by $\geq 50\%$ from PPD nadir and An increase in LDi or SDi from nadir 0.5 cm for lesions $\leq 2$ cm 1.0 cm for lesions $> 2$ cm In the setting of splenomegaly, the splenic length must increase by $> 50\%$ of the extent of its prior increase beyond baseline (eg, a 15-cm spleen must increase to $> 16$ cm). If no prior splenomegaly, must increase by at least 2 cm from baseline New or recurrent splenomegaly
Extranodal lesions	New FDG-avid foci consistent with lymphoma at interim or end-of-treatment assessment	

Response and Site	PET-CT-Based Response	CT-Based Response
Nonmeasured lesions	None	New or clear progression of preexisting nonmeasured lesions
New lesions	New FDG-avid foci consistent with lymphoma rather than another etiology (eg, infection, inflammation). If uncertain regarding etiology of new lesions, biopsy or interval scan may be considered	Regrowth of previously resolved lesions A new node > 1.5 cm in any axis A new extranodal site > 1.0 cm in any axis; if < 1.0 cm in any axis, its presence must be unequivocal and must be attributable to lymphoma Assessable disease of any size unequivocally attributable to lymphoma
Bone marrow	New or recurrent FDG-avid foci	New or recurrent involvement

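### The Part B EFS definition counts new treatment as an event only if it is chemotherapy, so some patients rescued by other means after APVD would be scored event-free

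*Combined protocol and SAP*

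**What the plan says.** The Part B primary endpoint is 1-year EFS, and its definition reads the same in Section 2.2 (Part B), Section 3.1 and Section 7.1 (Part B): "An event will be defined as progression, biopsy proven recurrence, initiation of next line of chemotherapy, or death". Section 7.1 applies it to an expected 39 advanced-stage patients (19 from Part A, 20 from Part B). It calls the regimen potentially efficacious if 33 or more are event-free at 1 year. It adds that this need not mean statistical significance and that secondary endpoints will also be weighed.

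Other passages bear on how the treatment component is read:

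- Section 3.4 lists what relapsed patients go on to need: "salvage chemotherapy, high dose chemotherapy, autologous stem cell transplant, brentuximab-vedotin, nivolumab or pembrolizumab".
- Section 4.3.2, on treatments barred during protocol therapy, says: "This includes any chemotherapy, investigational agent, biologic agent or other anti-tumor agents. Radiation therapy is also prohibited".
- Section 6.1.1.4.3 has the investigator "review all new anti-neoplastic therapy initiated after the last dose of trial treatment", and Section 6.1.4.6 tracks subsequent therapy for up to 5 years.
- Appendix 3 places score 4 or 5 with reduced uptake under partial metabolic response and comments: "At end of treatment, these findings indicate residual disease". Metabolic progression in target lesions needs "Score 4 or 5 with an increase in intensity of uptake from baseline"; new FDG-avid foci consistent with lymphoma also count.
- Section 3.5.1 (Early activity of APVD) reports that "5 patients so far have had a positive PET at end of treatment". One of the five progressed. Of the other four it says: "These patients were either followed with serial imaging with resolution or underwent a biopsy".

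**The concern.** Part B uses EFS because PET after a checkpoint inhibitor may be falsely positive, so a positive end-of-treatment PET is deliberately not an event. Residual but reduced uptake is not progression either. For a patient in that position without a positive biopsy, the start of further treatment is the component that would record the clinician's judgement that APVD was not enough.

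That component covers chemotherapy only. Two patients with the same scan and the same decision to treat are scored differently according to what they are given, and a remission reached by radiation is credited to APVD. Leaving a treatment type out can remove events but cannot add any, so the effect runs one way, toward meeting the benchmark that is said to justify further study.

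**Working it through.** **Inputs.** From Section 7.1, Part B: n = 39, pass at 33 or more event-free, and the table of pass probabilities. The documents do not give the share of failures that would show only as non-chemotherapy rescue. Call it f; the values below are assumptions.

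**Reproducing the plan's table.** With X binomial(39, p), P(X ≥ 33) is:

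| True EFS p | Plan | Recomputed |
|---|---|---|
| 75% | 0.11 | 0.1112 |
| 80% | 0.31 | 0.3124 |
| 85% | 0.63 | 0.6328 |
| 90% | 0.91 | 0.9106 |

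The table is correct for a cutoff of 33 and is not in dispute.

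**Which patients are scored differently.** Consider residual, reduced uptake at end of treatment, with no progression, positive biopsy or death by 1 year:

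| Next step | Scored under the plan |
|---|---|
| Observation | event-free |
| Salvage chemotherapy | event |
| Radiation only | event-free |
| Brentuximab vedotin or PD-1 antibody only | event-free if chemotherapy is read as in Sections 3.4 and 4.3.2 |

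**Effect of one patient.** 1/39 = 2.6 percentage points. With one failure uncounted, 32/39 (82.1%) is reported as 33/39 (84.6%) and passes. With two, 31/39 (79.5%) does.

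**Effect on the chance of passing.** Let p be the true EFS when any new lymphoma treatment is an event. The counted EFS is q = 1 − (1 − p)(1 − f), and the chance of passing is P(Bin(39, q) ≥ 33).

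| p | f (assumed) | Failures missed, 39(1 − p)f | q | Chance of passing |
|---|---|---|---|---|
| 80% | 0 | 0 | 0.800 | 0.31 |
| 80% | 10% | 0.8 of 7.8 | 0.820 | 0.43 |
| 80% | 20% | 1.6 of 7.8 | 0.840 | 0.57 |
| 75% | 0 | 0 | 0.750 | 0.11 |
| 75% | 10% | 1.0 of 9.8 | 0.775 | 0.19 |
| 75% | 20% | 2.0 of 9.8 | 0.800 | 0.31 |

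The row f = 0 is the plan's own figure and applies if no such rescue occurs.

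**What the documents show about exposure.** Five patients were PET-positive at end of treatment among at most 29 enrolled: 5/29 = 17% (exact 95% CI 6% to 36%). The 29 include early-stage patients, and not all need have reached end of treatment. No rescue without chemotherapy is reported.

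**The case against.** The strongest reply is that this is a loose word with no documented effect. Five parts of it deserve an answer.

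- *Other components still catch most failures.* This stands. A reader might infer that anyone given radiation, brentuximab vedotin or a PD-1 antibody remains event-free. The definition does not support that: later progression, chemotherapy or death within the year counts, and a positive biopsy would plausibly be scored as recurrence, although persistent disease is not strictly recurrence.
- *The sponsor may mean next-line systemic therapy.* This stands in part. Sections 3.4 and 4.3.2 list biologic agents, the antibody-drug conjugate and PD-1 antibodies apart from chemotherapy. Section 4.3.3, however, speaks of the other chemo drugs alongside pembrolizumab, which can be read as placing pembrolizumab among them. So the protocol cannot be said to use the word narrowly throughout. No reading brings in radiation, which Section 4.3.2 bars only during protocol therapy.
- *The group at risk looks larger than it is.* This stands. Scaling 5/29 to 39 patients gives 6.7, and a reader might take about 7 as the number exposed. Of the five, one progressed and is already an event; the other four are described as imaged to resolution or biopsied. Scaling the one in five who progressed gives 6.7 × 1/5 = 1.3, or 17% of the 7.8 failures expected at true EFS 80%. Even that requires all of them to escape every other component. Five patients of unstated stage cannot fix a rate in either direction.
- *Counting more treatment brings PET-driven events back.* This is a true cost, but the plan already accepts it for chemotherapy.
- *The benchmark is not a test and does not decide alone.* This stands. Section 7.1 also weighs secondary endpoints, and subsequent therapy would be on record for those deciding.

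**Conclusion.** The concern holds as a gap in the primary endpoint definition with a known direction and an unknown size. It is certain for radiation and probable for brentuximab vedotin or a PD-1 antibody. It applies only to patients with no other qualifying event within 1 year.

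The rise from 0.31 to 0.43 or 0.57 at true EFS 80% is illustrative. It rests on assumed shares of 10% and 20%, and on taking EFS with any new lymphoma treatment as the truth. Shares of 25% or 33% would give 0.63 or 0.74, but nothing in the documents supports failures being missed that often. Nor do the documents show that Part A results are already inflated: no non-chemotherapy rescue is reported, and if none occurs the count is unchanged. The case for acting rests on the one-way direction, the small margin at 33 of 39 and the low cost of repair.

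**What to change.** In Sections 2.2 (Part B), 3.1 and 7.1 (Part B), replace the chemotherapy component with: *initiation of any new treatment for persistent, progressive or recurrent lymphoma (systemic therapy, including an antibody-drug conjugate or off-protocol PD-1 antibody; radiation; or transplant)*. State that two things are not events: consolidative radiation planned before the end-of-treatment PET, and completing the planned first-line course with AVD or ABVD without progression. Apply the 33 of 39 rule to this count, and report the chemotherapy-only count as a sensitivity result.

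The cost is an amendment to one component in three places. Subsequent therapy is already reviewed and tracked (Sections 6.1.1.4.3 and 6.1.4.6). The one item to make sure of is a dated record of any plan for consolidative radiation.

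The downside is that radiation or a drug switch prompted by a falsely positive PET becomes an event; the sensitivity count shows how much that matters. The wider treatment list can only lower the event-free count, so adopting it with some Part A outcomes known does not favour the regimen. The AVD or ABVD exemption could raise the count only if someone would have scored that continuation as a next line, so patients covered by it should be listed.
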